14.3.9 T2 lesion volume

Analysis (Analysis Set)	Derivation	Statistical Analysis Methods	Missing data handling
Tertiary endpoint: Change from Baseline in T2 lesion volume			
Tertiary (FAS)	The absolute volume and change from Baseline to the Month i Visit, where i= 12, 24, in T2 lesion volume by Visit	Descriptive summary statistics.	

14.3.10 Magnetization Transfer Ratio (MTR)

Analysis (Analysis Set)	Derivation	Statistical Analysis Methods	Missing data handling
Tertiary endpoint: Change from Baseline in MTR percentage			
Tertiary (FAS)	Change from Baseline in MTR - White Matter (%) at Month 24 Visit.	Mixed-effects linear model for the change from Baseline with the following adjusting factors: 
 • Baseline score, • Age (in years), • EDSS at Baseline (≤ 3, > 3), • Time between scans (years), • Within-subject correlation. Estimated Least Square Means (LS Means) and corresponding Standard Errors (SE) will be presented by Visit including 2-sided p-values and 95% CI	Missing observations at Baseline: Subjects with a missing Baseline MTR will not be included in the linear model. Missing post-Baseline observations: Missing post-Baseline assessments will not be imputed. The repeated measurement model handles missing post-Baseline assessments under the assumption of MAR.
	Change from Baseline in MTR - Grey Matter (%) at Month 24 Visit.		
	Change from Baseline in MTR - T1 lesions (%) at Month 24 Visit.		
	Change from Baseline in MTR - T2 lesions (%) at Month 24 Visit.		
	Change from Baseline in MTR - T2 perilesions (%) at Month 24 Visit.		
	Change from Baseline in MTR - Putamen (%) at Month 24 Visit.		
	Change from Baseline in MTR - Thalamus (%) at Month 24 Visit.		
	Change from Baseline in MTR - Optic Nerve (%) at Month 24 Visit.		
Tertiary endpoint: Change from Month 6 Visit in MTR percentage			
Tertiary (FAS)	Change from Month 6 Visit in MTR - White Matter (%) at Month 24 Visit.	Descriptive summary statistics.	
	Change from Month 6 Visit in MTR - Grey Matter (%) at Month 24 Visit.		
	Change from Month 6 Visit in MTR - T1 lesions (%) at Month 24 Visit.		
	Change from Month 6 Visit in MTR - T2 lesions (%) at Month 24 Visit.		
	Change from Month 6 Visit in MTR - T2 perilesions (%) at Month 24 Visit.		
	Change from Month 6 Visit in MTR - Putamen (%) at Month 24 Visit.		
	Change from Month 6 Visit in MTR - Thalamus (%) at Month 24 Visit.		
	Change from Month 6 Visit in MTR - Optic Nerve (%) at Month 24 Visit.		

Mixed-effects linear model for repeated measures

As defined in Section 14.3.1 applying adaptations to the endpoints, factors and covariates listed in the table above.

14.3.11 Brain Volume

Brain volume will be provided for Baseline, Month 6 Visit, and Month 24 Visit by central reading for the following volume types:

- Brain Volume (BV), i.e. the total brain volume
- White Matter BV (WMBV)
- Grey Matter BV (GMBV)
- Deep Grey Matter BV (DGMBV)

Percentage brain volume change (PBVC) will be provided for BV from joint image comparison of the central reading for the following changes:

- Baseline to Month 1, 2, 3, 6, 12, 24 Visits
- Month 6 Visit to Month 24 Visit

Percentage white matter / grey matter / deep grey matter volume change from Baseline to Month 24 will be calculated as follows:

- $PWMVC = 100 * (WMBV \text{ at Month 24 Visit} - WMBV \text{ at Baseline}) / (WMBV \text{ at Baseline})$.
- $PWGVC = 100 * (GMBV \text{ at Month 24 Visit} - GMBV \text{ at Baseline}) / (GMBV \text{ at Baseline})$.
- $PWDGVC = 100 * (DGMBV \text{ at Month 24 Visit} - DGMBV \text{ at Baseline}) / (DGMBV \text{ at Baseline})$.

The annualized percentage brain volume change will be calculated by dividing percentage brain volume change by the actual length of follow up between the 2 MRI scans:

- $\text{Annualized PBVC} = (PBVC * 365.25) / (\text{Duration between the 2 MRI scans in days})$
- $\text{Annualized PWMBVC} = (PWMBVC * 365.25) / (\text{Duration between the 2 MRI scans in days})$
- $\text{Annualized PGMBVC} = (PGMBVC * 365.25) / (\text{Duration between the 2 MRI scans in days})$
- $\text{Annualized PDGMBVC} = (PDGMBVC * 365.25) / (\text{Duration between the 2 MRI scans in days})$

Brain Atrophy is defined by a Brain Volume Loss (BVL) of at least 0.4% during the Treatment Period, i.e.

Yes: annualized PBVC for Baseline to Month 24 \leq -0.4%

No: annualized PBVC for Baseline to Month 24 > -0.4%

If PBVC for Baseline to Month 24 Visit is missing it will be replaced by PBVC for Baseline to Month 12 Visit and if still missing by Baseline to Month 6 Visit, provided the last available assessment is at least 166 days (6 months * 30 days -14 days for Visit Window) after Baseline.

The same cut-off will also be applied for PWMBVC, PGMBVC, and PDGMBVC at Month 24 Visit.

Analysis (Analysis Set)	Derivation	Statistical Analysis Methods	Missing data handling
Tertiary endpoints: Annualized percentage brain volume change from Baseline			
Tertiary (FAS)	Annualized PBVC at Month i Visit, where i=1, 2, 3, 6, 12 and 24.	Mixed-effects linear model for repeated measures for the change from Baseline with the following adjusting factors: 
 • Baseline value, • Age (in years), • EDSS at Baseline (≤ 3, > 3), • Visit, • Time between scans (years), • Within-subject correlation. Estimated Least Square Means (LS Means) and corresponding Standard Errors (SE) will be presented by Visit including 2-sided p-values and 95% CI.	Missing observations at Baseline: Subjects with a missing Baseline brain volume will not be included in the linear model. Missing post-Baseline observations: Missing post-Baseline assessments will not be imputed. The repeated measurement model handles missing post-Baseline assessments under the assumption of MAR.
	Annualized PBVC 
 • $\leq -0.4\%$ • $> -0.4\%$ during the Treatment Period.	Descriptive summary statistics.	
Tertiary endpoints: Annualized percentage white matter brain volume change from Baseline			
Tertiary (FAS)	Annualized PWMBVC at Month 24 Visit.	Descriptive summary statistics.	
	Annualized PWBVC 
 • $\leq -0.4\%$ • $> -0.4\%$ at Month 24 Visit.		

Tertiary endpoints: Annualized percentage grey matter brain volume change from Baseline			
Tertiary (FAS)	Annualized PGMBVC at Month 24 Visit.	Descriptive summary statistics.	
	Annualized PGMBVC 
 • ≤ -0.4% • > -0.4% at Month 24 Visit.		
Tertiary endpoints: Annualized percentage deep grey matter brain volume change from Baseline			
Tertiary (FAS)	Annualized PDGMBVC change at Month 24 Visit.	Descriptive summary statistics.	
	Annualized PDGMBVC 
 • ≤ -0.4% • > -0.4% at Month 24 Visit.		
Tertiary endpoints: Percentage brain volume change from Baseline			
Tertiary (FAS)	PBVC change at Month 24 Visit.	Descriptive summary statistics.	
Tertiary endpoints: Percentage white matter brain volume change from Baseline			
Tertiary (FAS)	PWMBVC change at Month 24 Visit.	Descriptive summary statistics.	
Tertiary endpoints: Percentage grey matter brain volume change from Baseline			
Tertiary (FAS)	PGMBVC change at Month 24 Visit.	Descriptive summary statistics.	
Tertiary endpoints: Percentage deep grey matter brain volume change from Baseline			
Tertiary (FAS)	PDGMBVC change at Month 24 Visit.	Descriptive summary statistics.	
Tertiary endpoints: Percentage Brain Volume change from Month 6 Visit			
Tertiary (FAS)	PBVC at Month 24 compared to Month 6	Descriptive summary statistics.	
Tertiary endpoints: Brain volume			
Tertiary (FAS)	BV at Baseline, Month 6 and 24 Visits.	Descriptive summary statistics.	
Tertiary endpoints: White matter brain volume			
Tertiary (FAS)	WMBV at Baseline, Month 6 and 24 Visits.	Descriptive summary statistics.	
Tertiary endpoints: Grey matter brain volume			
Tertiary (FAS)	GMBV at Baseline, Month 6 and 24 Visits.	Descriptive summary statistics.	

Tertiary endpoints: Deep grey matter brain volume			
Tertiary (FAS)	DGMBV at Baseline, Month 6 and 24 Visits.	Descriptive summary statistics.	

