4.3.1 Tertiary Endpoints

Safety:

- Occurrences of treatment-emergent adverse events (TEAEs) and serious adverse events (SAEs) including and up to 24 months

Clinical:

- Changes in Symbol Digit Modality Test (SDMT) outcome at the end of 6, 12, 18 and 24 months compared to baseline
- Disability evolution as measured by EDSS/KFS, 9-Hole Peg Test (9HPT), Timed 25-Foot Walk (T25FW) at the end of 6, 12, 18 and 24 months compared to baseline
- ARR between baseline and 24 months
- Changes in CUA lesions during the following post-baseline periods compared to baseline period (i.e. the period from screening to baseline):
 - Period of month 6 to month 12
 - Period of month 1 to month 12
 - Period of month 18 to month 24
 - Period of month 1 to month 24

Further periods and comparisons may be defined in the SAP

- Number of CUA lesions during the baseline and post-baseline periods
- Changes in active T1 Gd+ lesion count at the end of 1, 2, 3, 6, 12, 15, 18 and 24 months compared to baseline
- Volume changes of T1 Gd+ lesions at the end of 1, 2, 3, 6, 12, 15, 18 and 24 months compared to baseline
- Number of T1 hypointense lesions at the end of 1, 2, 3, 6, 12, 15, 18 and 24 months compared to baseline
- Change in volume of T1 hypointense lesions at the end of 1, 2, 3, 6, 12, 15, 18 and 24 months compared to baseline
- Changes in new T2 lesion count during the post-baseline periods compared to the baseline period as defined above
- Responder rate during the different periods as defined above with responder being defined as subjects with a CUA lesion count reduction of at least 1
- Changes in T2 lesion volume at the end of 12 and 24 months compared to baseline
- Changes in Magnetization Transfer Ratio (MTR) at the end of 1, 2, 3, 6, 12, 15, 18 and 24 months compared to baseline
- Changes in brain volume at the end of 1, 2, 3, 6, 12 and 24 months compared to baseline (and changes at 24 months compared to 6 months to exclude pseudo-atrophy)
- No Evidence of Disease Activity (NEDA) at 24 months
- No Evidence of Progression or Active Disease (NEPAD) at 24 months

CCI [REDACTED]

[figure not shown]

5 Investigational Plan

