14.3.12 No Evidence of Disease activity

No Evidence of Disease activity (NEDA), also referred to as freedom from disease activity, is a new goal that is emerging in MS treatment. NEDA is a composite measure of disease activity, including relapses, cognition and disability progression, and MRI activity. Since MRI activity is a broad concept, which can correspond to the MRI lesion load or changes in brain volume monitoring brain atrophy, the distinction between NEDA-3 and NEDA-4 will be provided.

NEDA-3

NEDA-3 at Month 24 is defined by the absence of:

- Qualifying Relapses,
- 6-months Confirmed Disability Progression (6MCDP),
- MRI activity,

during the whole Treatment Period. If the information for one of the components is unknown, and none of the other components are observed, NEDA-3 will be classified as “unknown”. Thus, NEDA-3 can be derived from its components as follows:

- Yes: all components = “No”,
- No: at least one of the components =” Yes”,
- Unknown: Otherwise.

NEDA-3 (frequent MRI)

NEDA-3 at Month 24 is defined by the absence of:

- Qualifying Relapses,
- 6-months Confirmed Disability Progression (6MCDP),
- MRI activity (frequent MRI),

during the whole Treatment Period. If the information for one of the components is unknown, and none of the other components are observed, NEDA-3 will be classified as “unknown”. Thus, NEDA-3 can be derived from its components as follows:

- Yes: all components = “No”,
- No: at least one of the components =” Yes”,
- Unknown: Otherwise.

NEDA-4

NEDA-4 at 24 Month is defined as the composite endpoint of NEDA-3 and the absence of brain atrophy.

NEDA-4 (frequent MRI)

NEDA-4 (frequent MRI) at Month 24 is defined by the composite endpoint of NEDA-3 (frequent MRI) and the absence of brain atrophy.

Qualifying Relapse

- Yes: qualifying relapses reported during the Treatment Period,
- No: study completed, and no qualifying relapse reported during Treatment Period,
- Unknown: otherwise.

6-Months Confirmed Disability Progression (6MCDP)

A Sustained Increase in EDSS score, is defined by an increase of:

- at least 1.5 points if the Baseline EDSS score was 0, or
- at least 1 point if Baseline EDSS score was between 0.5 and 4.5 inclusively, or
- at least 0.5 point if the Baseline EDSS score was at least 5,

that occurs over a 6-month time Period.

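### The SAP's Brain Atrophy flag runs from Baseline, with Month 12 and Month 6 fallbacks at one annualized cut-off, so it depends on follow-up length and lacks the protocol's Month 6 reference

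*SAP*

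**What the plan says.** The protocol's brain-volume endpoint (Synopsis, 4.3.1 and 8.3.3) compares several visits with baseline and adds, in parentheses, "changes at 24 months compared to 6 months to exclude pseudo-atrophy".

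SAP 14.3.11 does the following:

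- It opens the definition with "Brain Atrophy is defined by a Brain Volume Loss (BVL) of at least 0.4% during the Treatment Period", then makes it operational as "annualized PBVC for Baseline to Month 24" at or below -0.4%.
- It annualizes by "dividing percentage brain volume change by the actual length of follow up between the 2 MRI scans".
- It gives a first fallback: "If PBVC for Baseline to Month 24 Visit is missing it will be replaced by PBVC for Baseline to Month 12 Visit". A second fallback, used when Month 12 is lacking too, takes the Month 6 value as long as that scan came 166 days or more after Baseline.
- It obtains Month 6 to Month 24 PBVC from central reading. The analysis table lists this as "PBVC at Month 24 compared to Month 6", with descriptive statistics only.

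In SAP 14.3.12, "NEDA-4 at 24 Month is defined as the composite endpoint of NEDA-3 and the absence of brain atrophy". That section refers back to 14.3.11 for atrophy but uses strictly below -0.4%. Brain Atrophy is also analysed alone there, by logistic regression. The SAP's modification history shows that NEDA-4 entered in version 3.0.

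**The concern.** By choosing Month 6 as the reference for its pseudo-atrophy comparison, the protocol treats volume loss before Month 6 as possibly not true atrophy. All three intervals that can set the SAP flag start at Baseline and contain that phase. The Month 6 fallback consists of nothing else, and annualizing roughly doubles it.

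Two things are at stake. Early loss of the kind the protocol wanted to set aside can be counted as atrophy. And two subjects with the same course can be classified differently only because one lacks a later scan.

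Fallback use is not confined to missed scans. Under SAP Section 9, a subject whose Course 2 is delayed by more than 3 months or never starts has all later efficacy data counted as missing. That subject loses Month 24 and moves to an earlier interval, usually Month 12.

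**Working it through.** **The plan's own figure.** Minimum interval for the Month 6 fallback: 6 × 30 - 14 = 166 days, as stated.

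**Inputs from the SAP.** Annualized PBVC = PBVC × 365.25 / days between scans (14.3.11). Cut-off 0.4% per year. Visit months of 30 days (Section 9), so Month 6, 12 and 24 fall at 180, 360 and 720 days, and Month 6 to 24 spans 540. A substituted value is taken to be annualized over its own scan pair, as the formula implies.

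**Inputs assumed, because the documents give none.** A one-off early loss *a* (%), complete by Month 6, and an underlying loss *r* of 0.1 to 0.3% per year, which is below the cut-off.

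**Formulas.** For an interval of *d* days starting at Baseline, annualized loss = *r* + *a* × 365.25/*d*. With no assumption about its source, the raw loss that trips the flag is 0.4 × *d*/365.25. The early loss that trips it on top of *r* is (0.4 - *r*) × *d*/365.25. For Month 6 to 24, *a* drops out.

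| Interval | Days | 365.25/*d* | Raw loss at cut-off | *a* needed, *r* = 0.1 / 0.2 / 0.3 | Added per year by *a* = 0.2% |
|---|---|---|---|---|---|
| Baseline to M6, minimum | 166 | 2.20 | 0.18% | 0.14 / 0.09 / 0.05% | 0.44% |
| Baseline to M6 | 180 | 2.03 | 0.20% | 0.15 / 0.10 / 0.05% | 0.41% |
| Baseline to M12 | 360 | 1.01 | 0.39% | 0.30 / 0.20 / 0.10% | 0.20% |
| Baseline to M24 | 720 | 0.51 | 0.79% | 0.59 / 0.39 / 0.20% | 0.10% |
| M6 to M24 | 540 | 0.68 | 0.59% | not affected | 0 |

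**One subject.** With *a* = 0.3% and *r* = 0.2% per year, the annualized loss is 0.2 + 0.15 = 0.35% at Month 24 (no atrophy), 0.2 + 0.30 = 0.50% at Month 12 (atrophy), 0.2 + 0.61 = 0.81% at Month 6 (atrophy), and 0.20% on Month 6 to 24 (no atrophy).

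**Illustrative share flagged.** Assume true loss is normal with mean 0.2% and SD 0.2% per year, and PBVC measurement error has SD *e* per scan pair. With *y* = *d*/365.25, share = 1 - Φ[(0.4 - 0.2 - *a*/*y*) / √(0.2² + (*e*/*y*)²)], with *a* = 0 for Month 6 to 24.

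| *a* | *e* | Baseline to M6 | Baseline to M12 | Baseline to M24 | M6 to M24 |
|---|---|---|---|---|---|
| 0 | 0 | 16% | 16% | 16% | 16% |
| 0.2% | 0 | 85% | 51% | 31% | 16% |
| 0 | 0.3% | 38% | 29% | 21% | 24% |
| 0.2% | 0.3% | 63% | 50% | 35% | 24% |

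The third row shows that measurement error alone makes the shorter Baseline intervals flag more often. Dependence on follow-up length therefore does not need pseudo-atrophy.

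**Reach into NEDA-4.** NEDA-3 'Yes' needs a completed study without a qualifying relapse, and lesion results from late visits or periods: T1 Gd+ at Month 18 or 24, and active T2 over Months 12 to 18 or 18 to 24. A subject on the Month 6 fallback must meet all of that yet lack PBVC at both Month 12 and Month 24. Other fallback subjects are mostly NEDA-3 'No' or 'Unknown' already. The SAP gives no 'Unknown' rule for NEDA-4. If it follows the NEDA-3 rule, fallback atrophy turns 'Unknown' into 'No', while an early leaver without atrophy stays 'Unknown' and is excluded from the regression. The fallback could then only lower the NEDA-4 rate.

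**Cut-off wording.** A value of exactly -0.4% is atrophy in 14.3.11 and not in 14.3.12. A loss of 0.4% over the Treatment Period is also not 0.4% per year: over 720 days the annualized rule needs 0.79%, nearly twice as much.

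**The case against.** The strongest reply is that the SAP does what the protocol asks. The pseudo-atrophy remark belongs to the brain-volume endpoint, whose main comparison is with baseline. The SAP has the Month 6 to 24 change centrally read and reports it. Protocol 7.3.4 names no atrophy component in NEDA. A reader might infer that the SAP breaches a protocol rule for NEDA-4; the documents do not support that, because the protocol has no such rule. What stands is that a safeguard was not extended to a composite the SAP added.

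A reader might also infer that many treatment responders will be scored as NEDA-4 failures. That is not supported either. The documents give no size for pseudo-atrophy, no true atrophy rate, no PBVC error and no count of missing Month 24 scans. Nor does eligibility guarantee active inflammation on MRI: it can be met by two relapses with no MRI criterion, and SAP 8.2 allows for subjects with no CUA lesions in the Baseline Period.

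Finally, the NEDA-3 components cover the whole Treatment Period, so moving the main atrophy definition to Month 6 would mix windows and discard true early loss. That is a fair argument against replacing the definition, or deleting the Month 12 fallback. It is not an argument against a second version. The endpoints are tertiary and exploratory, and Brain Atrophy and NEDA-3 are reported beside NEDA-4, which limits the harm.

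**Conclusion.** The concern holds as a weakness in a derived tertiary endpoint. The trigger of about 0.20%, 0.39% or 0.79% raw loss, according to the last usable scan, follows from the SAP's formula and 30-day months alone. The effect of pseudo-atrophy on top of that is conditional: for an assumed underlying loss of 0.1 to 0.3% per year, the early loss that tips a subject over is 0.59 to 0.20% at Month 24, 0.30 to 0.10% at Month 12 and 0.15 to 0.05% at Month 6. How many subjects would be misclassified cannot be stated, and the shares shown above are illustrations only.

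The effect falls mainly on the stand-alone Brain Atrophy regression. For NEDA-4 it works against the drug, and the Month 6 fallback contributes little. The inequality mismatch is editorial, but the two readings of the 0.4% need correcting in any case.

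**What to change.** In SAP 14.3.11 and 14.3.12, before the final database lock:

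1. Add a pre-specified version of Brain Atrophy and NEDA-4 based on annualized Month 6 to Month 24 PBVC, reported alongside the Baseline to Month 24 version.
2. Delete the Baseline to Month 6 fallback and class those subjects as 'Unknown'. Keep the Month 12 fallback, but report how many subjects rely on it.
3. Use one inequality in both sections, and state that the 0.4% is a rate per year rather than a loss over the Treatment Period.

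The cost is SAP wording and one more derived flag, from data that central reading already supplies. Slightly fewer subjects will be evaluable. The Month 6 to 24 version does not count true loss in the first 6 months. Its shorter interval also makes it somewhat noisier than Baseline to Month 24 (24% against 21% flagged in the illustration with measurement error and no early loss). Those are reasons to show both versions.

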8.3.3 Tertiary Endpoints

Safety:

- Occurrences of TEAEs and SAEs including and up to 24 months

Clinical:

- Changes in SDMT outcome at the end of 6, 12, 18 and 24 months compared to baseline
- Disability evolution as measured by EDSS/KFS, 9HPT, T25FW at the end of 6, 12, 18 and 24 months compared to baseline
- ARR between baseline and 24 months
- Changes in CUA lesions during the following post-baseline periods compared to the baseline period (i.e. the period from screening to baseline):
 - Period of month 6 to month 12

- Period of month 1 to month 12
- Period of month 18 to month 24
- Period of month 1 to month 24

Further periods and comparisons may be defined in the SAP

- Number of CUA lesions during the baseline and post-baseline periods as defined above
- Changes in active T1 Gd+ lesion count at the end of 1, 2, 3, 6, 12, 15, 18 and 24 months compared to baseline
- Volume changes of T1 Gd+ lesions at the end of 1, 2, 3, 6, 12, 15, 18 and 24 months compared to baseline
- Number of T1 hypointense lesions at the end of 1, 2, 3, 6, 12, 15, 18 and 24 months compared to baseline
- Change in volume of T1 hypointense lesions at the end of 1, 2, 3, 6, 12, 15, 18 and 24 months compared to baseline
- Changes in new T2 lesion count during the post-baseline periods compared to the baseline period as defined above
- Responder rate during the different periods as defined above with responder being defined as subjects with a CUA lesion count reduction of at least 1
- Changes in T2 lesion volume at the end of 12 and 24 months compared to baseline
- Changes in MTR at the end of 1, 2, 3, 6, 12, 15, 18 and 24 months compared to baseline
- Changes in brain volume at the end of 1, 2, 3, 6, 12 and 24 months compared to baseline (and changes at 24 months compared to 6 months to exclude pseudo-atrophy)
- NEDA at 24 months
- NEPAD at 24 months

CCI

CCI

CCI

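### Brain volume by visit is modelled only as an annualized rate, so a one-off early shift would appear as atrophy that slows from visit to visit

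*SAP*

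**What the plan says.** The protocol states the endpoint as a change, not a yearly rate: "Changes in brain volume at the end of 1, 2, 3, 6, 12 and 24 months compared to baseline" (Protocol 4.3.1; also 8.3.3). It adds a second contrast, "changes at 24 months compared to 6 months to exclude pseudo-atrophy" (Protocol 8.3.3).

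In SAP 14.3.11, central reading supplies percentage brain volume change (PBVC) for "Baseline to Month 1, 2, 3, 6, 12, 24 Visits" and for Month 6 to Month 24. The annualized version is "calculated by dividing percentage brain volume change by the actual length of follow up between the 2 MRI scans", with the factor 365.25. The only by-visit model listed is a repeated-measures model for "Annualized PBVC at Month i Visit, where i=1, 2, 3, 6, 12 and 24". It reports LS means by visit with SEs, two-sided p-values and 95% CIs.

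Un-annualized PBVC has two rows, both descriptive: "PBVC change at Month 24 Visit" and "PBVC at Month 24 compared to Month 6". SAP Section 7, on changes from the protocol, does not name a move from change to rate for brain volume.

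**The concern.** Dividing by elapsed time gives a meaningful rate only if loss builds up roughly in proportion to time. A step that occurs once, early, and then stops does not. Annualized, it is multiplied by about 12 at Month 1 and halved at Month 24, so the by-visit curve falls towards zero even though nothing changes after the step.

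The protocol gives a reason to expect such a step, because it builds in a Month 24 versus Month 6 contrast against pseudo-atrophy. The primary objective is onset of action, so early by-visit curves will attract attention. What is at stake is the reading of the trend: a reader could take the divisor's shape for a slowing of atrophy on treatment.

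**Working it through.** Neither document gives an expected brain volume change, a reading-error SD or a power figure for this endpoint, so there is no plan figure to reproduce.

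**Inputs from the documents.** The annualization formula is in SAP 14.3.11. A scheduled month is 30 days, and a duration is the date difference plus 1 day (SAP Section 9). The visit window is ±7 days (Protocol Section 7). N is about 265 (Protocol synopsis). The SAP atrophy cut-off is -0.4 %/year.

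**Assumptions, not in the documents.** One-off shift of -0.2% (range -0.1 to -0.5%) complete by Month 1; steady loss of 0 or 0.4 %/year; reading-error SD of 0.1 to 0.5% per comparison.

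**Formulas.** With D = 30 × month + 1:
- factor = 365.25 / D
- shift s alone, annualized = s × 365.25 / D
- shift plus steady loss r: change = s + r × D / 365.25; annualized = s × 365.25 / D + r

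| Month | D | Factor | Shift -0.2% only, %/year | Shift -0.2% and loss 0.4 %/year: change, % | Same, annualized, %/year |
|---|---|---|---|---|---|
| 1 | 31 | 11.78 | -2.36 | -0.23 | -2.76 |
| 2 | 61 | 5.99 | -1.20 | -0.27 | -1.60 |
| 3 | 91 | 4.01 | -0.80 | -0.30 | -1.20 |
| 6 | 181 | 2.02 | -0.40 | -0.40 | -0.80 |
| 12 | 361 | 1.01 | -0.20 | -0.60 | -0.60 |
| 24 | 721 | 0.51 | -0.10 | -0.99 | -0.50 |

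**Shift only.** The Month 1 to Month 24 ratio is 721 / 31 = 23.3, whatever the size of the shift. Across -0.1 to -0.5%, Month 1 reads -1.18 to -5.89 %/year and Month 24 reads -0.05 to -0.25 %/year. A shift of 0.4 × 31 / 365.25 = 0.034% at Month 1 is enough to equal the 0.4 %/year cut-off.

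**Shift plus steady loss.** The apparent slowing is 2.76 / 0.50 = 5.5-fold, although the rate after the step is constant. The un-annualized column shows a step and then a slope. From Month 6 to 24 the change is -0.4 × 540 / 365.25 = -0.59%, which recovers -0.4 %/year.

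**Steady loss only (s = 0).** The annualized value is -0.4 %/year at every visit. There is no artefact.

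**Visit window.** At Month 1, D ranges from 24 to 38 days, so the factor ranges from 15.2 to 9.6.

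**Each visit's test against zero.** Multiplying by a constant scales estimate and SE alike, so only variation in D within the window can alter the t statistic. A simplified simulation used 300 trials per scenario, N = 265, uniform ±7-day windows, independent errors and no +1 day. Under steady loss of 0.4 %/year, the median t at Month 1 was -5.3, -2.6 and -1.7 annualized, against -5.5, -2.7 and -1.7 un-annualized, for SDs of 0.1, 0.2 and 0.3%.

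**Does the model's time covariate remove the artefact?** SAP Section 9 measures it from the previous visit's scan, so after Month 1 it is not the divisor. In the same simulation with the shift and steady loss, the Month 1 mean was -2.87 to -2.90 %/year without a covariate, -2.84 to -2.87 with time from the previous scan, and -2.73 to -2.80 with time from Baseline. It does not.

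**The case against.** **The artefact is conditional.** It needs a one-off shift, and no shift size appears in either document. This stands, and the point is worded accordingly.

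**Noise.** A reader might infer that the early annualized values are mere noise because error is multiplied by about 12. The documents do not support that. The signal is multiplied too, and un-annualized Month 1 change is just as imprecise relative to its expected size. For the group mean, the 95% half-width from reading error alone at Month 1 is 1.96 × SD × 11.78 / √265, or 0.14 to 0.71 %/year for SDs of 0.1 to 0.5%. It reaches 0.4 %/year only at an SD of about 0.28%, and the documents give no SD.

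**Covariance.** A reader might also infer that Month 1 variance will inflate the later SEs. If the specification in SAP 14.3.1 carries over, the covariance is unstructured and allows a different variance at each visit. Harm would need a common-variance fallback, and the SAP leaves the fallback unspecified.

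**Un-annualized values may be shown anyway.** The introduction to SAP Section 14 promises by-visit descriptive statistics for efficacy endpoints and, where applicable, their components. That leaves room for un-annualized PBVC at Months 1 to 12 but does not name it, while 14.3.11 lists it for Month 24 only. So it is unclear rather than ruled out.

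**Pseudo-atrophy is already handled.** The Month 6 to 24 contrast gives a long-term reading free of an early step. That stands for the period after Month 6, but it does not repair the Month 1 to 3 rates or the trend across visits.

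**Small reach.** The analysis is exploratory and tertiary, and no between-visit contrast is planned. The atrophy variable uses Month 24, then Month 12, then Month 6, and needs at least 166 days, so Months 1 to 3 cannot enter it or NEDA-4. All of this stands.

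**Conclusion.** The point holds in conditional form. The only modelled by-visit analysis is on a scale that differs from the protocol endpoint, and on that scale a one-off early shift becomes a rate falling as 1/time. The apparent slowing is about 23-fold for a shift with no further loss, and about 5.5-fold for an assumed -0.2% shift on top of 0.4 %/year. What can mislead is comparison between visits and the size of the early values, not the test at any one visit.

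A reader might conclude that the planned analysis will show a false slowing. The documents do not support that: under steady loss the annualized means are flat. The conclusion rests on an early shift occurring, which the protocol anticipates but does not quantify. It is a minor matter, worth correcting because the correction is cheap.

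**What to change.** In the SAP 14.3.11 table, apply the existing repeated-measures model to un-annualized PBVC from Baseline at Months 1, 2, 3, 6, 12 and 24, as the protocol words the endpoint.

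State that annualized PBVC at Months 1 to 3 is not to be interpreted as an atrophy rate. Keep annualized rates for the longer intervals, in line with the SAP's own 166-day minimum for the atrophy variable. Read the long-term rate from Month 6 to Month 24, because an annualized Month 6 value from Baseline still doubles any early step.

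Cost: one additional model and one table row. No new data are needed, since central reading already supplies PBVC for every visit concerned.
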